Version Date: 3/2/2018

Principal Investigator: [name]

Co-Investigator: [name]

Study Physician: [name]

Study Title: Body Fat Reducing Effect and Safety of Enzymatically Modified Isoquercitrin in Overweight and Obese Subjects

I. Aim and Hypotheses

Specific Aim 1: To compare the body fat reducing effect of 360mg/day enzymatically modified isoquercitrin (EMIQ) with that of a placebo.

Hypothesis 1: Compared to a placebo, participants receiving EMIQ supplementation will have a greater reduction in total body fat as evidenced by measures of whole body DXA scan, skinfold thickness, waist to hip circumference ratio, resting metabolic rate, plasma adiponectin levels, physical activity, and dietary intake.

Specific Aim 2: To determine the safety of long term intake of EMIQ.

Hypothesis 2: Long-term intake of EMIQ has no ill effect on participant health as evidenced by measures of heart, liver, kidney function, and psychological state.

II. Background and Rationale

Dietary quercetin is a natural bioactive polyphenol with potential health benefits and the capacity to prevent development of various diseases including those of the cardiovascular system, central nervous system and others [1-3]. It is widely distributed in various plant foods such as onions, broccoli, concord grapes, apples and more [4]. In plants, quercetin is present as conjugated with different forms of glucosides [5], which affect their bioavailability. The bioavailability of different forms of quercetin has been the subject of several investigations [6]. Enzymatically-modified isoquercitrin (EMIQ) is a mixture of quercetin monoglucoside and its α -oligoglucosides, which mainly consist of quercetin-3-O- β -glucoside (Q3G) and α -glucosyl derivatives with 1-7 of additional linear glucose moieties [7, 8]. Supplementing the diet of apoE-deficient mice with EMIQ increased quercetin levels and suppressed atherogenesis in this mouse model of human atherosclerosis[9]. In human trials, the bioavailability of EMIQ

has been shown to be 17-fold higher than quercetin aglycone [10]. After efficient absorption of EMIQ, quercetin is released, and it exerts its biological activity such as reducing body fat, improving cardiovascular health and reducing blood pressure.

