To calculate number of subjects needed per group and provide 80% power at $\alpha=0.05$ we used mean differences and standard deviation (EMIQ: 19 ± 24.62 and Placebo: 1 ± 12.87) of whole abdominal fat loss from an early published study conducted in Japan, where the Japanese volunteers consumed 275mg EMIQ per day for 12 weeks and showed a positive impact of EMIQ on reduction of fat depots. We plugged in data from that study into this formula $N=1+[16(xS^2/d^2)]$ to calculate sample size. Using this formula the number of subjects in each group were calculated to be $n=18$. However, we selected to use 25 subjects per group which increases power of study to $>85\%$. 25 subjects per group is a conservative sample size, which make us to expect a larger difference in the means with a higher dose of EMIQ intake.

The primary objective of this study is to demonstrate reduction of total body fat following 12 weeks of EMIQ intervention. Therefore, we will determine statistically if EMIQ is effective to reduce percent body weight, total abdominal fat, subcutaneous and visceral fat after 12 weeks of intervention compared to baseline values. We plan to compare the two group medians with the Mann-Whitney U test. After reviewing the data at the completion of the study, we can assume normality, then we will compare the two group means with parametric t-test.

C. Subject Characteristics

Inclusion Criteria:

- Male or female age 18-65 years.
- Premenopausal female with regular menstrual cycle or post-menopausal female with cessation of menstrual cycle for a minimum of 6 months.
- BMI in the range of 26.0-37.0_
- Beck Depression Inventory Score less than 20.
- Fluency in spoken or written English.
- Willingness to be randomized to take EMIQ or placebo.
- Must weigh at least 164lbs

Exclusion Criteria:

- Any major illness or condition that may interfere with study outcomes at the discretion of the study physician.
- Diabetes Type I & Type II, or use of any pharmacological treatment for diabetes.
- Use of medications that interfere with energy metabolism
- Receiving hormone therapy growth hormone, testosterone, or estrogen with the exception of hormone contraceptives.
- GI diseases, conditions or medications known to influence GI absorption including active peptic ulcer disease or inflammatory bowel disease such as

- ulcerative colitis, Crohn's disease, celiac disease, chronic diarrhea or constipation.
- Undergone gastric bypass or other bariatric weight loss procedure.

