- [name] will regularly monitor potential risks and procedures in order to protect participants from risk.
- Will discuss any adverse events with the study physician on a weekly basis.
- Will report any adverse events associated with participation in the study protocol and file all required annual paperwork with the IRB.
- Will evaluate the progress of the study including periodic assessments of data quality and timeliness, recruitment, enrollment and retention, protocol violations, unanticipated events, volunteer risk vs. benefit, and anything else that may have an impact on the study outcome.
- Maintain vigilance of developments outside of the study that could affect participant's safety.
- Perform, at minimum, two reviews of the data per year to ensure safety and efficacy of the study.
- Responsibility for all procedures performed.
- Reviews all data as it may relate to volunteer safety. This includes factors like participant retention and reason for drop-out.
- Reporting all serious adverse events regardless of their relation to the study protocol.
- Provide the IRB with summaries of all adverse events.
- At the discretion of [name], the Co-I, [name], or [name], the study may be terminated at any time if the risks to study subjects are found to outweigh the potential benefits.

Additionally, no personal results will be communicated to study participants. However, participants will be informed of any necessary new findings developed during the course of this research study. Written results may be given directly, or mailed, to participants if they are still in the study, or mailed to them if they have completed their participation in the study.

H. Outcome

Our goal is to assess the safety and efficacy of EMIQ as it relates to body fat reduction. We predict that there will be no changes in health, and that there will be a significant difference between change in total body fat between the treatment and placebo groups.

I. Tissue Banking Considerations

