## Statistical Analysis Plan

All subjects who completed the study were included in the analysis. Summary statistics were expressed in mean  $\pm$  S.D. for continuous variables, and counts (percentage %) for categorical variables. Differences between treatment groups were tested using Student's *t*-test. Two-sample Wilcoxon test is used when variables appear to violate distributional assumptions. Model assumptions were assessed within an ANCOVA model predicting 12 week outcome, adjusting for baseline. Fisher's exact test or chi-square test was performed for categorical variables. An  $\alpha$  level of  $p < 0.05$  was considered statistically significant. Statistical analysis was conducted in R 3.4 (R Core Team 2017, Vienna Austria).

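### The plan tests four efficacy outcomes at p < 0.05 each, with no order, adjustment or rule for mixed results, so the 5% error rate does not cover the efficacy claim as a whole

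*SAP*

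**What the plan says.** The SAP (Statistical Analysis Plan) states that "Differences between treatment groups were tested using Student's" t-test, with a Wilcoxon test where distributional assumptions fail, and that p < 0.05 "was considered statistically significant". It names no primary endpoint, testing order or multiplicity adjustment.

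The protocol describes the efficacy question in four places:

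- Section III.B gives the objective: "The primary objective of this study is to demonstrate reduction of total body fat following 12 weeks of EMIQ intervention".
- The next sentence of III.B asks whether EMIQ works to "reduce percent body weight, total abdominal fat, subcutaneous and visceral fat after 12 weeks of intervention". Total body fat is not on that list.
- Section III.H predicts that "there will be a significant difference between change in total body fat between the treatment and placebo groups".
- Hypothesis 1 in section I says that a greater fat reduction will be shown by "whole body DXA scan, skinfold thickness, waist to hip circumference ratio, resting metabolic rate, plasma adiponectin levels, physical activity, and dietary intake".

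Neither document says whether one, some or all of these must be significant. Neither says whether the tests are one- or two-sided.

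**The concern.** An objective is not a decision rule. Suppose total body fat shows no difference but visceral fat gives p = 0.04. The SAP would call the visceral result significant, and section III.B lists visceral fat among the outcomes on which effectiveness is judged. Nothing in the text prevents that result from being presented as showing that EMIQ works, and nothing says that it should be. With several outcomes each tested at 0.05, the overall chance of a false finding exceeds the 0.05 used to design the trial. A reader of the results could not tell a planned confirmatory finding from the most favourable of several. Naming a primary endpoint would not settle this alone; the plan also needs to say what the remaining tests may be used for.

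**Working it through.** **Inputs from the documents.** Alpha is 0.05 per test (SAP). There are k = 4 outcomes in the III.B list, of which 3 are fat depots. The design has 25 per group. The planning values, for whole abdominal fat loss, are 19 (SD 24.62) against 1 (SD 12.87), a difference d = 18.

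**Inputs that are assumed.** Correlation between outcomes is not given; I use 0, 0.5 and 0.8. Two-sided testing is not stated, but the sample-size formula points to it. Of the earlier Japanese study the protocol says "We plugged in data from that study into this formula", and that formula has the constant 16. For 80% power, 2(1.96 + 0.84)² = 15.7 two-sided, whereas one-sided testing would give 12.4.

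**The plan's own figures first.** N = 1 + 16S²/d².
- With S as the simple mean of the two SDs, (24.62 + 12.87)/2 = 18.75, N = 18.35, which matches the stated 18.
- With the root-mean-square SD, 19.64, N = 20.06.
- At 25 per group the t-based power is 91% (mean SD) or 89% (root-mean-square SD). The stated figure of more than 85% holds, for one test of whole abdominal fat.

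**Error over several tests, no true effect on any outcome.** With independent outcomes:
- any significant difference, either direction: 1 − 0.95⁴ = 18.5% for four outcomes; 1 − 0.95³ = 14.3% for three
- a significant difference favouring EMIQ: 1 − 0.975⁴ = 9.6% for four; 1 − 0.975³ = 7.3% for three

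For correlated outcomes I used 1,000,000 simulated sets of equally correlated normal test statistics with cut-off 1.96.

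| Event | Correlation 0 | 0.5 | 0.8 | One test |
|---|---|---|---|---|
| 4 outcomes, either direction | 18.5% | 15.6% | 11.4% | 5% |
| 4 outcomes, false reduction | 9.6% | 7.8% | 5.7% | 2.5% |
| 3 depots, either direction | 14.3% | 12.5% | 9.8% | 5% |
| 3 depots, false reduction | 7.3% | 6.3% | 4.9% | 2.5% |

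The inflation for four outcomes is 11.4/5 = 2.3 to 18.5/5 = 3.7 times in either direction, and 5.7/2.5 = 2.3 to 9.6/2.5 = 3.8 times for a false reduction. For the three depots the false-reduction inflation is 4.9/2.5 = 2.0 to 7.3/2.5 = 2.9 times.

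**Check with related depots.** If abdominal fat is modelled as subcutaneous plus visceral fat, with a correlation of 0.7 to 0 between those two, the three depots give 8.7-11.4% in either direction and 4.3-5.8% for a false reduction.

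**Effect of two remedies.**
- A Bonferroni threshold of 0.05/4 = 0.0125 brings the either-direction error to 4.9% at independence and 3.2% at correlation 0.8. Power for abdominal fat at 25 per group falls from 89% to 74% (t-based, root-mean-square SD).
- A single confirmatory test keeps 5%, or 2.5% for a false reduction, with no adjustment of its threshold.

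**The case against.** The strongest objection is that the plan never says one significant result is enough. Sections I and III.B join their outcomes with a plain conjunction; if all had to be significant, the overall error would not exceed 5%. This stands in part: a success rule based on any one outcome is an inference, and the fair statement is that the rule is missing. But requiring all outcomes is not stated either, and the figures show what is at stake if the gap is filled in the permissive way.

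Second, total body fat is already the stated objective and the subject of the prediction in section III.H. That is true and makes the remedy easy, but section III.B then moves to a list that omits it, and the SAP repeats neither.

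Third, the depots come from the same DXA data (section III.E, Overview), so independence is implausible and the upper ends of the ranges are unlikely. This stands; the lower ends and the related-depots check are the better guide.

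Two stronger readings are tempting and are not supported:

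- A reader might take 11-19% as the chance of falsely claiming that EMIQ reduces a fat depot. It also counts results where EMIQ looks worse, and one of the four outcomes, percent body weight, is not a depot. Under two-sided testing the false-reduction chance is about half as large and must be compared with 2.5%.
- A reader might count all seven Hypothesis 1 measures, which gives 30% if independent (1 − 0.95⁷). Those include diet and physical activity, which participants are asked to keep as usual and which are largely monitored for that purpose. A chance difference in diet would not show that EMIQ reduces fat.

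Finally, one part of the SAP was not available for this review, so the absence of error control is judged on the Statistical Analysis Plan text and the protocol.

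**Conclusion.** The gap is real and should be closed, but its size needs careful statement. The either-direction and false-reduction rates in the table are conditional: they apply if any one significant result may carry the claim, if tests are two-sided, and if no outcome is truly affected. Within that, the four-outcome error is roughly two to four times the single-test rate; for the three depots, when treated as related, it is nearer twice. The documents do not show that the investigators intend to claim success on any single depot. They show only that the plan would not stop it.

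**What to change.** State in the SAP that the confirmatory efficacy claim rests only on the between-group difference in change in total body fat at 12 weeks, tested at two-sided 0.05. This agrees with the objective in section III.B and the prediction in III.H. State also that percent body weight, the abdominal, visceral and subcutaneous depots and the other Hypothesis 1 measures are supportive or exploratory, reported as estimates with 95% confidence intervals and no stand-alone efficacy claim. Align the list in III.B with this.

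A fixed testing order for the depots after total body fat is optional. It is valid only if set before unblinding. The SAP is written in the past tense, so its timing should be recorded; if results are already known, the depots should be labelled exploratory instead.

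The cost is a few sentences, with no new data and no change in sample size. There are two drawbacks. Depot results, including whole abdominal fat, on which the sample size was based, could not support the efficacy claim alone. And the documents give no expected effect or SD for total body fat, so the stated power does not carry over to the confirmatory test; the SAP should say so.
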